## **2.4 Sample Size**

No formal statistical calculation of sample size will be used for this Phase 1/2a study. The sample size is empirical. The small numbers per cohort in this study are not intended for statistical hypothesis inference analysis. Results from this study will be utilized in sample size calculations for subsequent studies.

This study will involve approximately 30 eligible normal healthy volunteers in NHV cohorts and a minimum of 60 and a maximum of 84 CHB patients in CHB cohorts. Each of the 5 NHV cohorts will recruit 6 healthy volunteers. CHB cohorts 1b, 1c, 2b, 3b, 4b and 5b will recruit a minimum of 4 and a maximum of 8 patients, and CHB cohorts 6, 7, 8, 9, 10, 11 will recruit a maximum of 4 CHB patients. Cohort 12 will recruit 12 CHB patients.

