### 3. STATISTICAL CONSIDERATIONS

Data will be handled and processed according to the sponsor's representative (Novotech (Australia) Pty Ltd) Standard Operating Procedures (SOPs), which are written based on the principles of GCP.

All data collected on the eCRFs will be presented in the data listings and will be listed and sorted by subject number and visit, where applicable. All summaries will present the data by ARO-HBV dose level/cohort and overall (total subjects), as applicable.

Data collected during the main study (up to the Day 29 or Day 113 EOS visits) and at the additional follow-up visits (CHB cohorts only) will be presented in the same summary table, as appropriate. The first part of each table will present the main study results for the specific analysis. The second part of each table will include all data collected during the study, including data collected during the follow-up period, for the subset of CHB patients that consented to participate in the follow-up. All data will be included in the listings, and data collected during the follow-up period will be flagged in all event/medication-based listings. Separate figures that include all data will be presented for the subset of patients that participated in the follow-up period.

Unless otherwise stated, the following statistical approaches will be taken:

- Continuous variables: Descriptive statistics will include the number of non-missing values (N), mean, standard deviation (SD), median, minimum, maximum.
- Categorical variables: Descriptive statistics will include frequency counts and percentages per category. Percentages will be rounded to one decimal place, with the denominator being the number of subjects in the relevant population with non-missing data, unless otherwise specified.
- Imputation: No missing data will be imputed generally.
- Confidence intervals (CIs): CIs will be two-sided and will use 95% confidence levels unless specified otherwise.
- Baseline: Baseline values will be defined as the last non-missing observation (pre-dose value closest to the first dose) for each subject prior to the dosing of study medication (i.e. start of injection on Day 1).
- Repeat assessments (Safety): If there is a repeat test, the repeat result will be used in the analysis table and the original result will only be listed in the data listing.

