### Virology Responses

The following virology responses are also defined based on the qualitative response data:

- Anti-HBsAg seroconversion is defined as the absence of HBsAg (i.e. a 'Not Detected' result for HBsAg which is defined as a value less than 0.05 IU/mL) and the presence of Anti-HBsAg (i.e. a 'Detected' result for Anti-HBsAg). Patients will be analyzed as non-responders (seroconversion = 'No') at a specific time point if the HBsAg result at that time point is reported as equal to or greater than 0.05 IU/mL ('Detected').
- Anti-HBeAg seroconversion is defined as the change from HBeAg 'Detected' to HBeAg 'Not Detected' and the presence of anti-HBeAg (i.e. a 'Detected' result for anti-HBeAg). Patients will be analyzed as non-responders (seroconversion = 'No') at a specific time point if the HBeAg result at that time point is reported as 'Detected'. Anti-HBeAg seroconversion is only applicable to HBeAg positive patients.

For each of the response endpoints, frequent count and percentage will be summarised for each category of qualitative HBsAg, anti-HBsAg, anti-HBsAg seroconversion, HBeAg, anti-HBeAg and anti-HBeAg seroconversion response by cohort for all the assessed study visits. The exact (Clopper-Pearson) 95% confidence interval for each category (response) will be reported as well.

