### Time to Event Endpoints

- Time to HBsAg Loss is defined as the duration from first dosing to the date of HBsAg 'Not Detected' (HBsAg loss defined as HBsAg < 0.05 IU/mL). Subjects without HBsAg loss will be censored at the end of study (or the end of follow-up period).
- Time to anti-HBsAg seroconversion is defined as the duration from first dosing to the date of anti-HBsAg seroconversion. Subjects without anti-HBsAg seroconversion will be censored at the end of study (or the end of follow-up period).
- Duration of Response (for HBV DNA, qHBsAg, qHBeAg, qHBcrAg, qHBV RNA): defined as the duration from post dose nadir back to within 20% of baseline value. The analysis will only be performed for the overall study period (including the follow-up period) and only patients with baseline values above the LLQ for the specific parameter will be included in the analysis. Subjects with the endpoint not returning to within 20% of baseline value will be censored at the end of the follow-up period.

The time to event endpoints will be analyzed by survival analysis method. Survival analysis will only be conducted if there are at least some responders within a cohort. The survival functions of the time to event endpoints will be summarized for 25th percentile, median, and 75th percentile and their 95% confidence intervals. The rates of HBsAg Loss and anti-HBsAg seroconversion at Day 60 and Day 113 post dosing (and also at Days 169, 225, 281, 337 and 393 for the subset of CHB subjects that participated in the follow-up), the response rates (for HBV DNA, qHBsAg, qHBeAg, qHBcrAg, qHBV RNA) at Day 30 and Day 60 (and additional time points at 30 days intervals as appropriate) post nadir, and their respective 95% confidence intervals will be derived based on their survival functions estimated by Kaplan-Meier method. In addition, the graphs of Kaplan-Meier estimates of survival functions (survival plots) will be presented. Histograms will also be presented showing the response rates for each cohort over 30-day intervals.

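### Kaplan-Meier 95% intervals for landmark rates collapse or vanish whenever a small cohort's estimate is 0 or 1, and the duration-of-response rates have no exact interval to fall back on

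*SAP*

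**What the plan says.** SAP section 11, Time to Event Endpoints, fixes the landmarks. The first set is "The rates of HBsAg Loss and anti-HBsAg seroconversion at Day 60 and Day 113 post dosing", with Days 169, 225, 281, 337 and 393 added for patients in follow-up. The second set is the duration-of-response rates for HBV DNA, qHBsAg, qHBeAg, qHBcrAg and HBV RNA, "at Day 30 and Day 60 (and additional time points at 30 days intervals as appropriate) post nadir". For both sets the rates "and their respective 95% confidence intervals will be derived based on their survival functions estimated by Kaplan-Meier method". No variance estimator, transformation or rule for an estimate of 0 or 1 is given. SAP section 3 adds only that "CIs will be two-sided and will use 95% confidence levels unless specified otherwise".

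The analyses are run by CHB cohort. SAP section 2.4 gives 4 to 8 patients for cohorts 1b, 1c and 2b to 5b, and 12 for cohort 12. For the rest, "CHB cohorts 6, 7, 8, 9, 10, 11 will recruit a maximum of 4 CHB patients". Duration of response is further limited to patients whose baseline exceeds the LLQ for that marker.

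Two other provisions bear on the point. The first is a gate: "Survival analysis will only be conducted if there are at least some responders within a cohort". The second is in SAP section 11, Virology Responses, which covers qualitative HBsAg, anti-HBsAg and seroconversion by cohort at every assessed visit: "The exact (Clopper-Pearson) 95% confidence interval for each category (response) will be reported as well". That provision has no gate and does not cover duration of response.

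**The concern.** A Kaplan-Meier interval takes its width from the events seen so far. Before the first event, and after the last patient at risk has had the event, the data give Greenwood's formula nothing usable. In large samples this touches only the ends of the curve. In cohorts of 4 to 12 it can cover several pre-specified landmarks.

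A table reading 100% (100 to 100) for four patients would claim a certainty the data cannot give, and a blank would leave the reader with no measure of precision. SAP section 2.4 says results will be used in sample size calculations for later studies, so the reported precision has a use beyond this report.

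**Working it through.** **Inputs.** Cohort sizes are from SAP section 2.4. The 95% two-sided level is from SAP section 3. Landmarks, gate and interval source are from SAP section 11. The event times below are illustrative.

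**Cohort sizes against the SAP total.** Minimum: 6×4 + 6×4 + 12 = 60. Maximum: 6×8 + 6×4 + 12 = 84. Both match SAP section 2.4 (taking cohorts 6 to 11 at 4 each). The SAP states no precision figure to reproduce.

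**Formulas.** With d events among r at risk at each event time, S(t) = Π(1 − d/r) and g(t) = Σ d/[r(r − d)]. The plain interval is S ± 1.96·S·√g. The log-log interval is S raised to the power exp(±1.96·√g/|ln S|).
- If S = 1, then g = 0. The plain interval has zero width, and the log-log form divides by ln 1 = 0.
- If S = 0, the last event has d = r, so g divides by zero and no interval exists.

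**HBsAg loss, a cohort that passes the gate.** Take one loss at Day 225, with the rest censored at Day 393. At Days 60, 113 and 169, S = 1 and g = 0. The loss rate is 0%, with a plain interval of 0 to 0 and no log-log interval, whether n is 4, 8 or 12. From Day 225 an interval exists. For n = 4, S = 0.75, g = 1/(4×3) = 0.0833 and √g/|ln S| = 0.2887/0.2877 = 1.003, which gives these rates:

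| n | Loss rate from Day 225 | Log-log 95% interval |
|---|---|---|
| 4 | 25.0% | 3.9 to 87.2% |
| 8 | 12.5% | 1.9 to 61.3% |
| 12 | 8.3% | 1.2 to 46.1% |

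**Duration of response.** Take n = 4, with returns to within 20% of baseline at Days 40, 60, 80 and 100 after nadir.
- Day 30: S = 1, so the interval has zero width or is undefined.
- Day 60: S = 0.5, log-log interval 5.8 to 84.5%.
- Day 100 onward: S = 0, no interval.

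The visit schedule makes S = 1 at Day 30 plausible. In Protocol Table 1.5 the follow-up visits are 56 days apart, each ±5 days. The shortest scheduled gap between two of them is 56 − 5 − 5 = 46 days. From Day 113 (±2) to Day 169 (±5) it is 164 − 115 = 49 days. A patient whose nadir falls at Day 113 or later therefore has no scheduled visit in the next 30 days at which a return could be seen. If every nadir in a cohort falls there, S = 1 at Day 30 follows from the schedule.

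**Exact limits, no censoring before the landmark.** With no events the Clopper-Pearson upper limit is 1 − 0.025^(1/n). With all events the lower limit is 0.025^(1/n).

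| n | 0 of n | n of n |
|---|---|---|
| 4 | 0 to 60.2% | 39.8 to 100% |
| 8 | 0 to 36.9% | 63.1 to 100% |
| 12 | 0 to 26.5% | 73.5 to 100% |

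The LLQ restriction can reduce n further. For 0 of 3 the exact interval is 0 to 70.8%.

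**The case against.** The strongest reply is that HBsAg loss and seroconversion are already covered. The Virology Responses section gives exact intervals for every cohort at every assessed visit, including cohorts with no responders. While nobody has lost HBsAg, status at a visit and cumulative incidence are both 0/n. A cohort of four fully observed patients with its first loss at Day 225 would therefore show 0 to 60.2% at the Day 57, 113 and 169 visits. This stands, and it confines the problem for these two endpoints to a degenerate Kaplan-Meier figure beside a valid exact one. Visit status and cumulative incidence can differ once events occur, and Day 60 is not a scheduled visit, so the two outputs are not interchangeable throughout.

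A second reply is that a reader might infer that every time point with no events gets a false interval, and that this is the usual case. The documents do not support that. The gate removes cohorts with no responders from the survival output altogether. The chance of no event by a landmark is (1 − p)^n. At an assumed p of 10% it is 66%, 43% and 28% for n = 4, 8 and 12. At 30% it is 24%, 6% and 1%. Neither value of p is in the documents.

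A reader might also compute that the nominal 95% interval covers the truth only 29%, 53% and 69% of the time for n = 4, 8 and 12. Those figures assume p = 10% and no censoring, ignore the gate, and score every no-event sample as a printed zero-width miss. On the same assumptions, when the log-log interval exists it covers 85%, 93% and 96%. The SAP does not name the transformation, and a missing interval claims no certainty.

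Finally, SAP section 2.4 disclaims hypothesis testing, and none of these rates is a primary or secondary objective. This stands and limits the severity. It does not help duration of response, which has no second interval.

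**Conclusion.** The point holds in a limited form. In a cohort that passes the gate, any landmark where the Kaplan-Meier estimate is 0 or 1 gets a zero-width or undefined 95% interval under Greenwood's variance, in either the plain or the log-log form. It applies in full to the duration-of-response rates of the five markers. For HBsAg loss and seroconversion it is an inconsistency between two outputs, one of them sound.

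The size is the gap between a zero-width or blank interval and the exact limits in the table above, widest in the cohorts of four. Those limits assume no censoring before the landmark. A wider reading, that these endpoints go without valid intervals or that cohorts with no responders go unreported, is not supported, because the by-visit exact intervals cover all cohorts. The effect is on reported precision in a descriptive analysis. No test, dose decision or stopping rule depends on it. Severity is minor to moderate.

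**What to change.** In SAP section 11, Time to Event Endpoints, name the interval method for landmark rates. Use the exact Clopper-Pearson interval when nobody is censored before the landmark. Otherwise use an exact-type interval for the Kaplan-Meier estimate, such as the beta product confidence procedure. Apply this at least whenever the estimate is 0 or 1, with duration of response as the priority.

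For HBsAg loss and anti-HBsAg seroconversion, add a cross-reference from the time-to-event tables to the by-visit exact intervals, including those for cohorts with no responders.

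The cost is a few lines of SAP text and a short macro. No new data or visits are needed. The intervals will be wider than the degenerate ones they replace.

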## **12. CELLULAR IMMUNOLOGY**

For CHB cohorts in New Zealand, if feasible, cellular immunology data will be collected at Days 1 (pre-dose), 43 and 113.

Cellular immunology data will be analyzed using the PD Population. Descriptive statistics will be used for the summary. For continuous antibody measurement data, the observed value and change from baseline (last pre-dose value on Day 1) for each dose level (cohort) for all time points assessed will be summarised descriptively. In addition to other descriptive statistics, the summary statistics will also include geometric mean in the table. If categorical data (negative/positive) are reported, these values will be summarised as well for frequent count and percentage. Post-hoc exploratory data analyses maybe conducted depending on the data available.

All cellular immunology data will be presented in the by-subject data listings.

### **13. IMMUNOGENICITY**

For CHB cohorts (Cohorts 1b, 1c, 2b, 3b, 4b, 5b, 6, 7, 8, 9, 10,11 and 12) blood samples for anti-drug antibodies testing will be collected at pre-dose, day 57 and at the end of study visit (Day 113) or at early termination as per Schedule of Assessments. Anti-drug antibodies will be analyzed using the Safety Population.

Descriptive statistics will be summarised for anti-drug antibodies. For continuous antibody measurement data, the observed assay value and change from baseline (last pre-dose value on Day 1) for each dose level (cohort) for all time points assessed will be summarised descriptively. In addition to other descriptive statistics, the summary statistics will also include geometric mean in the table. If categorical data (negative/positive) are reported for antibody measurement data, these values will be summarised as well for frequent count and percentage.

All anti-drug antibodies measures will be presented in the by-subject data listings.

#### **14. CYTOKINES AND COMPLEMENT**

Cytokines Panel A (whole blood, NHV cohorts only) will be collected at the time of 0 (pre-dose), 15 min, 0.5, 1, 2, 3, 6, 24 and 48 hours post-dose. Cytokines Panel B (whole blood, CHB cohorts only) will be collected across the study period according to the protocol schedule of assessment,

Complement (serum and plasma, NHV cohorts only) will be collected at the time of 0 (pre-dose), 0.5, 2, 6 and 24 hours post-dose.

Cytokines (Panels A/B) and complement data will be analyzed using the PD Population. Descriptive statistics will be summarised for cytokines and complement parameters, including the observed value, change from baseline (last pre-dose value on Day 1) and percentage change from baseline for each dose level (cohort) for all time points assessed. In addition to other descriptive statistics, the summary statistics will also include geometric mean in the table.

Mean and individual subject assessment values of cytokines and complement parameters over time will be plotted.

All cytokines and complement data will be presented in the by-subject data listings.

**15. HANDLING OF MISSING DATA**

Missing values will not be imputed.

**16. CHANGES TO THE PLANNED ANALYSIS**

Any changes to the analyses outlined in the approved SAP will be detailed in the Clinical Study Report (CSR).

## **17. INTERIM AND FINAL ANALYSIS**

### **17.1 Dose Escalation, Data Safety Committee (DSC) Analyses**

Dose escalation will require approval by the DSC based on a review of all cumulative available safety data for prior cohorts. Based on observations for all NHV subjects in a cohort through Day 8, and experience from any prior cohorts, dosing will begin for the next NHV cohort and as applicable the next CHB cohort at the discretion of the DSC.

Escalation to the next highest dose level will proceed in cohorts of 6 until the dose level of 400 mg is completed, or the trial is halted prematurely by the PI, DSC or Sponsor due to safety or other concerns. Blinding will be preserved to the extent possible for the NHVs; however, treatment un-blinding may occur, at the PI's discretion, where deemed necessary for treatment of an AE or for a decision to be made regarding trial continuation.

A formal charter will be in place prior to study start and will establish the rules, meeting frequency and scope of responsibilities of the DSC.

### **17.2 Interim Analyses**

An interim analysis of the safety and PD data was planned and performed in May 2019 (data cut-off 27Mar2019). This interim analysis was conducted to assist with the planning of future studies and Health Authority interactions and did not impact the conduct of this study. The Sponsor was unblinded to selected summary data only.

A second interim analysis based on all study data up to Day 113 for all cohorts, was completed in February 2020 (data cut-off 14Nov2019).

### **17.3 Final Analysis (End of Study)**

The final end of study analysis will be based on the final version of the SAP. If feasible, Clinical Study Report analysis of quantitative HBsAg through EOS (Day 113) and Additional Follow-Up (Day 393) will be based on a final batched analysis of samples. PD analyses will be completed at EOS (Day 113) and at the end of additional follow up period only in subjects entering into the additional follow up period.

**18. SOFTWARE**

The following software will be used to perform the statistical analyses: SAS® Version 9.4 or higher (SAS Institute, Cary, North Carolina, USA).

## 19. TABLES

Tables will be produced separately for NHV cohorts (Cohorts 1, 2, 3, 4 and 5), CHB cohorts (Cohorts 1b, 1c, 2b, 3b, 4b, 5b, 6, 7, 8, 9, 10, 11 and 12), and the subset of CHB patients that participated in the follow up period.

No.	Title	Analysis Population	Day 113: Interim Analysis
14.1.1.1	Summary of Disposition	Safety	X
14.1.1.2	Summary of Demographics	Safety	X
14.1.1.3.1	Summary of Baseline Disease Characteristics	Safety	X
14.1.1.3.2	Summary of Baseline Virology Characteristics	PD	X
14.2.1.1	Summary of Plasma Concentrations of ARO-HBV (ng/mL) by Dose [NHV Cohorts 1, 2, 3, 4 and 5 only]	PK	X
14.2.2.1	Summary of Plasma Pharmacokinetic Parameters of ARO-HBV by Dose [NHV Cohorts 1, 2, 3, 4 and 5 only]	PK	X
14.2.2.2	Analysis of Dose Proportionality for ARO-HBV [NHV Cohorts 1, 2, 3, 4 and 5 only]	PK	X
14.2.3.1	Summary of Plasma Concentrations of ARO-HBV (ng/mL), Nucleos(t)ide and JNJ-6397 Plasma Concentrations (Cohort 12) [CHB Cohort 12 only]	PK	
14.2.4.1	Summary of Anti-drug Antibodies [CHB cohorts only]	Safety	
14.2.4.2.1	Summary of Quantitative HBV Assessments and Change from Baseline [CHB cohorts only]	PD	X
14.2.4.2.1.1	Summary of Quantitative HBV Assessments and Change from Baseline by Baseline HBV DNA Group [CHB cohorts only]	PD	X
14.2.4.2.1.2	Summary of Quantitative HBV Assessments and Change from Baseline by Baseline HBeAg Group [CHB cohorts only]	PD	X
14.2.4.2.2	Summary of Quantitative HBsAg (IU/mL) by IL28B Genotype and Change from Baseline [CHB cohorts only]	PD	
14.2.4.2.3	Summary of Quantitative HBV Assessments Change from Baseline Categories [CHB cohorts only]	PD	X
14.2.4.2.4	Summary of Qualitative HBV Assessments [CHB cohorts only]	PD	X
14.2.4.3	Summary of HBV Virology Response [CHB cohorts only]	PD	X
14.2.4.4	Summary of Time to HBsAg Loss [CHB cohorts only]	PD	X
14.2.4.5	Summary of Time to Anti-HBsAg Seroconversion [CHB cohorts only]	PD	X
14.2.4.6	Summary of Duration of Response for HBV DNA [CHB cohorts only]	PD	X
14.2.4.7	Summary of Duration of Response for HBsAg	PD	X

No.	Title	Analysis Population	Day 113: Interim Analysis
	[CHB cohorts only]		
14.2.4.8	Summary of Duration of Response for HBeAg [CHB cohorts only]	PD	X
14.2.4.9	Summary of Duration of Response for HBcrAg [CHB cohorts only]	PD	X
14.2.4.10	Summary of Duration of Response for HBV RNA [CHB cohorts only]	PD	X
14.2.4.11	Summary of Cellular Immunology Parameters [CHB cohorts in New Zealand only]	PD	
14.2.5.1	Summary of Cytokine Parameters [Panel A for NHV cohorts, Panel B for CHB cohorts]	PD	X
14.2.6.1	Summary of Complement Parameters [NHV cohorts]	PD	X
14.3.1.1	Summary of Concomitant Medications and Non-Drug Therapies	Safety	X
14.3.3.1	Overall Summary of Treatment Emergent Adverse Events	Safety	X
14.3.3.2	Summary of Treatment Emergent Adverse Events by System Organ Class and Preferred Term	Safety	X
14.3.3.3	Summary of Treatment Emergent Adverse Events in Descending Order of Frequency by Preferred Term	Safety	X
14.3.3.4	Overall Summary of Related Treatment Emergent Adverse Events	Safety	X
14.3.3.5.1	Summary of Related Treatment Emergent Adverse Events by System Organ Class and Preferred Term	Safety	X
14.3.3.5.2	Summary of JNJ-6379 Related Treatment Emergent Adverse Events by System Organ Class and Preferred Term (Cohort 12) [CHB Cohort 12 only]	Safety	X
14.3.3.6.1	Summary of Related Treatment Emergent Adverse Events in Descending Order of Frequency by Preferred Term	Safety	X
14.3.3.6.2	Summary of JNJ-6379 Related Treatment Emergent Adverse Events in Descending Order of Frequency by Preferred Term (Cohort 12) [CHB Cohort 12 only]	Safety	X
14.3.3.7	Summary of Treatment Emergent Adverse Events by System Organ Class and Preferred Term and by Severity	Safety	X
14.3.3.8	Summary of Treatment Emergent Adverse Events by System Organ Class and Preferred Term and by Relationship to Study Drug	Safety	X
14.3.3.9	Summary of Serious Treatment Emergent Adverse Events by System Organ Class and Preferred Term	Safety	X
14.3.3.10.1	Summary of Serious Study Drug Related Treatment Emergent Adverse Events by System Organ Class and Preferred Term	Safety	X

No.	Title	Analysis Population	Day 113: Interim Analysis
14.3.3.10.2	Summary of Serious JNJ-6379 Related Treatment Emergent Adverse Events by System Organ Class and Preferred Term (Cohort 12) [CHB Cohort 12 only]	Safety	X
14.3.3.11	Summary of Treatment Emergent Adverse Events Leading to Study Drug or Study Withdrawn	Safety	X
14.3.3.12	Summary of Treatment Emergent Adverse Events Occurring at the Treatment Injection Site	Safety	X
14.3.3.13	Summary of Treatment Emergent Adverse Events Fitting the Definition of Local Injection Site Reactions (LISR) (See LISR definition in Section 10.1)	Safety	X
14.3.3.14	Summary of Treatment Emergent Adverse Events Fitting the Definition of Local Injection Site Reactions (LISR) by System Organ Class and Preferred Term and by Severity	Safety	X
14.3.4.1	Laboratory – Hematology: Summary and Change from Baseline	Safety	X
14.3.4.2	Laboratory - Chemistry: Summary and Change from Baseline	Safety	X
14.3.4.3	Laboratory – Coagulation: Summary and Change from Baseline	Safety	X
14.3.4.4	Laboratory - Urinalysis: Summary and Change from Baseline	Safety	X
14.3.4.5	Summary of Haematology Shifts from Baseline	Safety	X
14.3.4.6	Summary of Biochemistry Shifts from Baseline	Safety	X
14.3.4.7	Summary of Coagulation Shifts from Baseline	Safety	X
14.3.4.8	Summary of Subjects with ALT above Upper Limit of Normal Over Time [CHB cohorts only]	Safety	X
14.3.5.1	Summary of Vital Signs	Safety	X
14.3.6.1	Summary of Physical Examination	Safety	X
14.3.7.1	Summary of ECG Values	Safety	X
14.3.7.2	Summary of ECG Findings	Safety	X

